9.5 Study Size

The NHS Digital database comprises data from the national registries of vaccination and hospitalization with linkage to the CMR, lab, and mortality data. It is the largest dataset possible for England and covers all regions. As of early March 2021, near 20 million people in England have been vaccinated with at least 1 dose of any COVID-19 vaccines. According to a recent study in Scotland (Vasileiou et al 2021), the Oxford/AstraZeneca vaccine have been used by the majority of the 75+ years old age group and by a significant proportion of the 60-65- and 70-75-years old age groups.

Based on the preliminary count of the cohort of VE from ORCHID in collaboration with PHE (N=5.4 million), as of 7/4/2021, 42.1% of the population have received a COVID-19 vaccine. Overall, 91% of people 80 years and older, 91% of people 65-79 years old, and 79% of people aged 16-64 years old in risk groups were vaccinated. Of those vaccinated, 38% has received the Oxford/AstraZeneca COVID-19 vaccine, i.e. more than 7 million people. It is expected that almost all of England's COVID-19 vaccination data are included in the NHS Digital databases representing the best option for this type of study. Given a large number of people vaccinated with the Oxford/AstraZeneca COVID-19 vaccine and the use of the national database, the study should have sufficient power to address the study objectives.

9.6 Data Management

As a first step, the quality of datasets will be evaluated, and only datasets recognised of sufficient quality will be used. All statistical analyses will use the R statistical software (Rproject, 2020). Full details will be provided in the SAP.

9.7 Data Analysis

9.7.1 Statistical Methods – General Aspects

A detailed SAP will be developed for this analysis. The SAP may modify the plans outlined in the protocol; any major modifications of primary endpoint definitions or their analyses would be reflected in a protocol amendment. For all study designs, p-values will be quoted to two decimal places, unless they are less than 0.001 (whereby the p-value will be given as < 0.001) or between < 0.005 and > 0.001, in which case they will be stated to three decimal places. Parameter estimates will be reported with 95% CIs. All statistical tests are 2 sided and with a 5% significance level.

A CONSORT 2010 Flow Diagram of the study population detailing each step of the inclusion and exclusion criteria applied will be generated. As indicated in section 9.4, to obtain the most followup data, the primary analysis will include all HES data until 8 weeks prior and all raw hospitalization data (SUS) from 8 weeks to 2 weeks prior database lock. A sensitivity analysis including only HES data, therefore a shorter follow-up for hospitalization, will also be done.

For the concurrent control arm, each week starting from 8th December 2020, we will match all newly vaccinated persons in a 1:1 ratio to unvaccinated controls (Dagan et al, 2021). Newly vaccinated persons will be eligible for inclusion in the study, even if they will have previously been selected as a control. We will match vaccine recipients and controls on variables associated with the probability of both vaccination and infection or severity of COVID-19: age (study defined age bands), gender, general practice, (or NHS Region), and comorbidity as defined by CMMS quartile. We will exact match each week (if feasible). To assess the quality of matching, love plots will be created showing the mean standardized difference between each vaccinated cohort (AstraZeneca or other vaccine cohort) and the comparator cohorts in participants' characteristics. If important differences are observed, the matching criteria will be refined.

The demographic and characteristics of study participants in each vaccine arm and its respective control arm at baseline will be determined during the 12-month period before index date using the measurement closest to index date.

Summary tables of all patient characteristics and end points indicated in section 9.3.2 will be created for both the before and after matching situation to provide insight in population characteristics as well as in errors and missingness. Categorical variables will be checked on meaningful categories and frequencies. It is not anticipated that categories will have too low frequency. Pooling will be considered when the frequency for a category becomes below 1000.

Continuous variables will be summarized in terms of min, max, interquartile range, median and mean to get insight in these variables, but also to provide a first indication of use of same unit across the database and to obtain a first impression about possible transformations needed. Missing values will be considered in detail. If the percentage of missingness is below 10%, complete case analyses will be performed. When exceeding 10%, multiple imputation will be run additionally based on the total dataset.

For each outcome event, the summary tables will present for each study cohort the number of first events, total person-years for the event and number of first events per person-years (rate), the RR and the VE which is calculated as 1 - RR. This will also be provided per age group and per frailty score where further stratification/subgroups are indicated below. Finally, VE will also be provided in shorter periods after dose 1, and between the doses, and presence of comorbidities.

Poisson regression with offset for time at risk will be used to estimate rates using the matched dataset, adjusting for the matching variables and BMI, smoking, prescribed medications, and frailty score, which are known to increase risk of hospitalization and death and are likely associated with vaccination.

Checks on linearity for continuous variables will be performed. In order to evaluate interactions of independent variables with the exposure (i.e. vaccinated/comparator), continuous variables will be categorized and the VE will be tabulated per category. For variables for which the maximum and minimum VE across categories is more than 10% different, interaction effects with the exposure will be taken into account in the Poisson model. For interactions among independent variables that are not the exposure, interaction variables will be created. Forward selection is performed, and interaction variables will be included when the computed VE changes with more than 10%.

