Outcome(s): The primary outcome is COVID-19 related hospitalization, Intensive Care Unit (ICU) admission, and death. Events due to any causes of these measures will be secondary. Additionally, the following outcomes will be secondary: any positive SARS-CoV-2 positive test, medically attended COVID-19, COVID-19 related emergency department visit, HCRU related to COVID-19 and associated cost, breakthrough case, time to vaccine waning, and long COVID.

Data sources: Linked secondary databases in England accessed through the Oxford-Royal College of General Practitioners Clinical Informatics Digital Hub (ORCHID) and National Health Services (NHS) Digital's Trusted Research Environments (TRE) will be used to assess VE. The primary care data will be linked with vaccination, hospitalization, COVID-19 test and mortality data at the national level for capture of key study variables. Data assets will be requested through the NHS Digital Data Access Request Service (DARS).

Study size: ORCHID contains records from 18 million people, over 30% of the English population, whilst NHS Digital database comprises complete national data from the national

registries of vaccination and hospitalization with linkage to the computerised medical record (CMR), lab, and mortality data. The NHS Digital dataset is the largest dataset possible for England and covers all regions. As of early March 2021, near 20 million people in England have been vaccinated with at least 1 dose of any COVID-19 vaccines and more than 7 million people have received the Oxford/AstraZeneca COVID-19 vaccine. Given this large number and the use of the national database, the study should have sufficient power to address the study objectives.

Data Analysis: To carry out the VE analysis, vaccinated persons will be matched each week (if feasible) to the unvaccinated individuals by age, gender, general practitioner (GP) practice (or NHS region), and comorbidity.

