The Hospital Episode Statistics (HES), Secondary Uses Service (SUS), General Practice Extraction Service data for pandemic planning and research (GDPPR), and Office of National Statistics (ONS) data may include information on COVID-19 infection through specific COVID-19 diagnosis codes. Using a combination of both COVID-19 SGSS/NPEX and diagnosis codes from HES, SUS, GDPPR, and ONS allow capturing the COVID-19 infection status for all study participants. Since testing for COVID-19 and its capture was not complete at the beginning of the pandemic but significantly improved later, restriction of the study period from July 2020 or the 2nd wave of infection by regions in England, whichever is later, for determining COVID-19 related events in the historical population is needed. Medically attended COVID-19 will come from ORCHID, GDPPR, Emergency Care Data Set (ECDS) and HES. Emergency department visits will come from ECDS. SARS-CoV-2 variants will come from COG UK. Data on HCRU and associated cost will come from HES using the Health Resource Grouper (HRG) and primary care attendance and medication costs. Long COVID will come from ORCHID and HES.

|--|

Variables		Data source	Comments
Hospitalization	Date	HES for curated data	6-8 weeks lag for HES
	Frequency	SUS for more recent raw data	SUS is updated weekly
	Duration	HES APC for combined	with a maximum of 2 weeks lag
ICU admission	Date	CC for ICU specific data	
	Frequency		
	Duration		
Death	Date	ORCHID/GDPPR for date	2 weeks lag
	Cause of death	ONS for cause of death	6 weeks lag
Medically attended COVID-19		ORCHID, GDPPR, ECDS, HES	
COVID-19 infection	Positive RT-PCR test; date	SGSS for first positive test in hospital and community NPEX for all positive/negative test in the community	Daily update
	ICD-10/SNOMED codes for COVID	HES, ONS, GDPPR	
SARS-CoV-2 variants of interest		COG UK	
Long COVID		ORCHID, HES	
HCRU and cost		HES & HRG	
		ICU datasets	
		Primary care attendance & costs	

APC: Admitted Patient Care; CC: Critical Care COG UK: COVID Genomics UK Consortium; ECDS: Emergency Care Data Set; GDPPR: General Practice Extraction Service data for pandemic planning and research; HES: Hospital Episode Statistics; HRG: Health Resource Grouper; ICU: Intensive Care Unit; NPEX: National Pathology Exchange; ONS: Office for National Statistics; ORCHID: Oxford-Royal College of General Practitioners Clinical Informatics Digital Hub; SGSS: COVID-19 Second Generation Surveillance System; SUS: Secondary Uses Service.

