9.4 Data Source(s)

This study will employ linked England's national databases for data on background characteristics, medications, comorbidities, COVID-19 infection status, vaccination status, hospitalization, ICU admission, and mortality. The datasets use unique identifiers allowing linkage across the datasets and avoidance of duplicates.

Through the NHS DARS it is possible to request access to a number of secondary data assets collected as part of routine care and commissioning activities in the NHS. With appropriate approval, these data assets are linkable in their TRE. Data assets available through DARS which may be used for this study include:

- General Practice Extraction Service (GPES) data for pandemic planning and research (GDPPR): central collection of GP patient data for COVID-19 purposes (fortnightly collection – All GP practices in England). Limitations of these data included: (1) Some practices may have poor data quality; (2) The clinical data are restricted to 56,318 concepts from the much larger SNOMED clinical terminology (SNOMED CT international version has 352,567 concepts, the UK version has additional concepts to meet national needs)(SNOMED, 2020). Careful testing will be required for the equivalence of variables between ORCHID and GDPPR. We will carefully compare descriptive statics for key variables, some measures such as Cambridge Multimorbidity Score (CMMS) will require careful validation in GDPPR as some of their component codes do not exist within GDPPR.
- NIMS includes 2 associated datasets including COVID-19 Vaccination Status and COVID-19 Adverse Reaction.
- HES: this is the transformed data, initially part of the Commissioning Data Set (CDS), covering patients attending accident and emergency (A&E) units, admitted for treatment,

or attending outpatient clinics at NHS hospitals in England, including details about length of stay and HRG to enable health economic analysis. An HRG is a grouping consisting of patient events that have been judged to consume a similar level of resource, which can be linked to an appropriate NHS tariff. Statistical controls have been applied to the HES products. Data on cost will be extracted from HES using HRG. (Time lag 8-12 weeks)

- ECDS: this collects data from A&E Departments (time lag 8-12 weeks). Only available for linkage to ORCHID.

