- Civil Registrations (Deaths): Information including the date, place and certificated cause of death from the Office for National Statistics (ONS) (Time lag 8-12 weeks, released by NHS Digital with HES)
- COVID-19 SGSS Demographic and diagnostic information from laboratory test reports for patients tested for COVID-19 in England only. It currently includes the first positive results from pillar 1 (swab testing in Public Health England (PHE) and NHS hospital labs and pillar 2 (swab testing for the wider population) (Time lag less than 1 week)
- COVID-19 UK Non-hospital Antigen Testing Results (Pillar 2) data includes a range of COVID19 test results, including NPEX. This is broadly similar to SGSS, but only covers Pillar 2 data, however, contains the full result set i.e. all positive, negative and null results.
- COVID-19 Hospitalization in England Surveillance System (COVID-19 SARI-Watch/CHESS): Epidemiological data on COVID-19 infection in persons requiring hospitalization in ICU or High Dependency Units. It records all demographic, risk factor, treatment and outcome information for patients admitted to hospital with a confirmed COVID-19 diagnosis. This only has data from a limited number of surveillance hospitals. (Time lag – less than 1 week)
- SUS Episodes (including the following concepts: Admitted Patient Care (APC), Outpatient, Critical Care & A&E). This covers all secondary care provided in England and paid for by the NHS. This is essentially the CDS. These data are transformed to create HES product set that is subject to official publication timelines. Therefore, SUS should be considered tactical but carries a shorter latency (Time lag –1-2 weeks). Only available for linkage to ORCIHD.

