- ORCHID a TRE for research and surveillance (de Lusignan, 2021). This TRE contains the Oxford-Royal College of General Practitioners (RCGP) Research and Surveillance Centre (RSC) one of Europe's oldest sentinel systems. The network has been expanded considerably during the SARS-CoV-2 pandemic. It pseudonymised data are linked to the range of data sets described above by NHS Digital, though usage must be approved on a study-by-study basis. It is one of the freshest (either daily or twice weekly data extracts) with data quality as good as it gets in primary care. The University of Oxford team run the national primary care surveillance system The Oxford-RCGP RSC. This surveillance system is sponsored by PHE and collaborates in reporting vaccine uptake and effectiveness, including of COVID-19 vaccine.

Additionally, the data on SARS-CoV-2 variants will be requested from the COG UK (Time lag – unknown).

Most individual data sources have frequent refresh (daily or weekly) and most have only 1–2-week lag from the time of data entry to when they are ready for analysis. One exception is the HES data source with the longest lag time of approximately 8-10 weeks. The raw hospitalization data source, SUS, which is the source of HES has much shorter time lag of 1-2 weeks. For this reason, our main analysis will include HES data until 8 weeks before the database lock. The sensitivity analysis will include HES data until 8 weeks before database lock.

Validation exercises will be conducted in the NHS Digital TRE, these are to ensure there is no denominator inflation and also to validate the GDPPR variables, as there are a limited number of concepts available. We will ensure the total population denominator is correct. The denominator varies across data sources therefore we will explore any areas of apparent list inflation. In addition, we will validate variables with a recorded prevalence in NHS Digital TRE within 15% of that in ORCHID, and validate or provide a surrogate marker for variables with >15% variation. Finally, we will choose and validate a multimorbidity measure ideally CMMS, but will consider using an alternative comorbidity measure if needed. The method for this exercise will be referenced in the Statistical Analysis Plan (SAP).

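### The primary hospitalization rule takes weeks 8 to 2 before lock from SUS, which Section 9.4 links only to ORCHID, and no text says where hospital person-time ends for everyone else

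*Protocol*

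**What the plan says.** **Source rule.** Protocol Section 9.7.1 has the primary analysis use "all HES data until 8 weeks prior and all raw hospitalization data (SUS) from 8 weeks to 2 weeks prior database lock". A HES-only sensitivity analysis, with correspondingly shorter hospitalization follow-up, is planned there. Section 9.7.3 extends it to ICU admission.

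**SUS linkage.** The SUS entry in Section 9.4 ends "Only available for linkage to ORCIHD". Earlier in the same section, a general sentence about the requested assets, a list that includes SUS, says that "these data assets are linkable in their TRE". Table 5 in Section 9.3.2 lists SUS as a hospitalization source with no restriction.

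**Coverage.** The synopsis states that "ORCHID contains records from 18 million people, over 30% of the English population". Section 9.5 rests the adequacy of the study size on the national database. Section 9.1 names both ORCHID and the NHS Digital environment and does not say which hosts the primary analysis.

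**HES lag.** Three values appear:
- Table 5: "6-8 weeks lag for HES"
- Section 9.4, HES entry: "Data on cost will be extracted from HES using HRG. (Time lag 8-12 weeks"
- Section 9.4, closing summary: "One exception is the HES data source with the longest lag time of approximately 8-10 weeks"

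**Rule as given in Section 9.4.** Section 9.7.1 refers back to Section 9.4. There the main analysis takes HES to 8 weeks before lock, without SUS in the rule, and then: "The sensitivity analysis will include HES data until 8 weeks before database lock".

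**End of follow-up.** Section 9.2.4 ends follow-up at end of study, deregistration, vaccination of the control, or death. The end of a person's linked hospital data is not listed. Section 9.7.1 uses time at risk as the Poisson offset.

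**The concern.** A rate is sound only if the denominator stops when the numerator can no longer be observed. On the protocol's own linkage statement, a person outside ORCHID has no stated source of hospital admissions in the last six weeks of the primary analysis, yet nothing stops that person's time at risk. ICU admission depends on the same sources. Hospitalization and ICU admission are two of the three primary outcomes, and Section 9.7.1 requires their rates to be reported by arm. Any shortfall falls on the most recent person-time, where booster follow-up is concentrated. The differences in service use and cost in Section 9.7.6.2 would not cancel a shortfall either, if they use the same splice.

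The switch from HES to SUS raises a second question. If HES is not complete at 8 weeks, there is a stretch before the switch where HES is partial and SUS is not used. This would affect the HES-only sensitivity analysis too.

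**Working it through.** **The protocol's own figure.** Section 9.5: 38% of near 20 million vaccinated people is 0.38 × 20 = 7.6 million, which agrees with its figure of more than 7 million. The protocol gives no event rate or precision calculation, so the rest uses its stated lags and coverage.

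**Inputs.**
- Window: 8 − 2 = 6 weeks (Section 9.7.1).
- ORCHID share s: at least 0.30 (synopsis). A rough upper value comes from Section 9.5: near 20 million vaccinated and 42.1% coverage imply 20 / 0.421 = 47.5 million people, and 18 / 47.5 = 0.38. The two counts have different dates, so this is only approximate.
- Start of matching: 8 December 2020 (Section 9.7.1). Booster announcement: 16 September 2021 (synopsis).
- Lock date: not shown, so assumed. The range 1 January to 31 March 2022 fits the first interim report in Section 9.12. End of 2022 is a late case.
- Assumptions: national cohort, person-time not cut by source, flat event rate, person-time spread evenly over calendar weeks.

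**Missed inside the window** = 1 − s: 1 − 0.30 = 70%; 1 − 0.38 = 62%.

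**Missed overall** = 6(1 − s) / F, where F is the weeks from start to lock, minus 2.

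| Assumed lock | F, all follow-up | 6/F | Missed | F, since booster announcement | 6/F | Missed |
|---|---|---|---|---|---|---|
| 1 Jan 2022 | 53.6 | 11.2% | 6.9–7.8% | 13.3 | 45.2% | 28.0–31.6% |
| 31 Mar 2022 | 66.3 | 9.1% | 5.6–6.3% | 26.0 | 23.1% | 14.3–16.2% |
| 31 Dec 2022 | 105.6 | 5.7% | 3.5–4.0% | 65.3 | 9.2% | 5.7–6.4% |

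**HES seam.** Weeks before the 8-week switch with possibly incomplete HES:
- lag 6–8 weeks: 0
- lag 8–10 weeks: up to 10 − 8 = 2
- lag 8–12 weeks: up to 12 − 8 = 4

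In the worst case nothing is captured in those 4 weeks. The overall loss for a first-quarter 2022 lock is then [6(1 − s) + 4] / F, which is 11.6% to 15.3%.

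**Effect on vaccine effectiveness.** Let w = 6/54 be the window share, and c_v and c_u the capture in the window for vaccinated and unvaccinated. The observed RR is RR × [(1 − w) + w·c_v] / [(1 − w) + w·c_u]. Take an illustrative RR of 0.20.
- Equal capture (0.30 in both): RR stays 0.200.
- c_v = 0.30, c_u = 0.35: overall RR 0.1988 (VE 80.1%); inside the window 0.2 × 0.30/0.35 = 0.171 (VE 82.9%).
- c_v = 0.35, c_u = 0.30: overall RR 0.2012 (VE 79.9%); inside the window 0.233 (VE 76.7%).

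The 30% and 35% captures are assumed; the protocol gives nothing on capture by arm.

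**The case against.** The strongest defence is that the loss depends on two things the protocol does not state: that the primary analysis runs on the national cohort, and that person-time continues past each person's last linked hospital data. An ORCHID-only cohort would have no gap from SUS linkage. Section 9.7.1 ties follow-up to source in the HES-only analysis and speaks of person-years for the event, so the authors may intend to truncate by source. This stands, and it makes the finding conditional. It does not remove it: Section 9.5 points to a national cohort, and the list in Section 9.2.4 contains no such truncation.

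A reader might infer that the primary effectiveness estimate is materially biased. The documents do not support that. Controls are matched 1:1 each week, and a vaccinated person is censored when the control is vaccinated, so the under-captured weeks fall largely on both members of a pair. ORCHID is a primary care network, so pairs from one practice should share linkage status. The permitted fallback to NHS Region gives no such assurance, but even the assumed imbalance above moves overall VE by only about 0.1 percentage point.

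A reader might also infer that HES is incomplete for everyone in weeks 8 to 12. That takes the longest of three conflicting lags as fact. Under Table 5 the 8-week switch is adequate, and under the closing summary of Section 9.4 the gap is at most 2 weeks.

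The HES-only sensitivity analysis removes the SUS problem for hospitalization and ICU, though not the seam. Death comes from other sources.

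**Conclusion.** Two contradictions hold on any reading. The SUS restriction in Section 9.4 conflicts with that section's general linkage sentence and sits uneasily with Table 5. And Section 9.4 gives the main and sensitivity analyses the same HES rule without SUS, against Section 9.7.1. The three HES lags are also inconsistent, and the 8-week switch is safe under only the shortest.

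The undercount is conditional. In a national cohort with uncut person-time, 62–70% of hospitalizations and hospital-data ICU admissions in the six-week window cannot be seen. Absolute rates then lose about 6–8% of all events for a first-quarter 2022 lock and about 4% for a lock at the end of 2022. For follow-up since the booster announcement the loss is 14–32% with a first-quarter 2022 lock. The ratio is unaffected if capture is equal in the two arms.

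A larger booster figure is tempting. Assuming a lock on 31 January 2022, booster time from 1 October 2021, 67–70% unlinked, and either constant or linearly rising person-time gives 26–44%. The lock date and uptake pattern are not in the documents, and boosters belong to an extension objective, so that range is only an illustration.

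This is not a detail to leave to the SAP: the protocol fixes the rule itself, and Section 9.7.1 says major changes to primary endpoint definitions or analyses would be reflected in an amendment.

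**What to change.** In Sections 9.4 and 9.7.1:

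1. Reconcile the SUS linkage restriction with the general linkage sentence and Table 5, and state which research environment hosts the primary analysis.
2. Reconcile the three HES lags and set the HES cut-off at the confirmed completeness date. If none can be confirmed, use the longest stated lag, 12 weeks; the SUS window then becomes 12 − 2 = 10 weeks.
3. End hospitalization and ICU person-time for both members of a matched pair at the date their linked source is complete. Use SUS to extend follow-up to 2 weeks before lock only in pairs where both members are SUS-linked. Add this to the end-of-follow-up list in Section 9.2.4.
4. Correct the main and sensitivity rules in Section 9.4 to match Section 9.7.1.

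The cost is wording and a linkage flag per person. With step 3 the loss from missing SUS linkage falls to zero. In exchange, people without SUS linkage, and anyone paired with them, lose the last six weeks of hospital follow-up, plus some partly observed HES weeks if the cut-off moves beyond 8 weeks.

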9.1 Study Design – General Aspects

The effectiveness objectives will be addressed through a retrospective cohort study using linked secondary databases in England accessed through ORCHID and NHS Digital's TRE. Persons vaccinated with Oxford/AstraZeneca COVID-19 vaccine or another COVID-19 vaccine will be compared to matched persons not vaccinated with any COVID-19 vaccine for occurrence of study outcomes.

Due to England's vaccination campaign starting with the older age group, as of March 22 2021, over 90% of people 70 years of age or older were vaccinated with at least one dose of any COVID-19 vaccine (Public Health England, 2021). Therefore, it is expected that the concurrent control arm will have considerable challenges. A greater proportion of younger people might be included who may have lower hospitalization and death (particularly because the Joint Committee of Vaccination and Immunisation (JCVI) recommended early vaccination of people 16 to 64 years with comorbidities). Additionally, people receiving terminal care and those who do not engage much with the health system may also be included. For these reasons, the concurrent control arm is matched with the vaccine arm by age and other characteristics. Events' rates will also be stratified by age groups (e.g. 12-15,16-49, 50-64, 65-69, 70-79, 80+).

We will also explore how COVID-19 vaccination in England coincided with the 3rd wave of COVID-19 and any subsequent wave that may occur. For this analysis, we will include vaccination data periods beyond February 2021.

There have been changes in the age groups vaccinated and the introduction of booster doses. The Moderna and Pfizer BioNTech vaccines have been licenced for children (Medicines and Healthcare products Regulatory Agency (a & b), 2021) and booster doses were introduced in the autumn of 2021. For these reasons the analyses will be extended to include the 12–16-year-old age-group and any booster vaccination (9)(Department of Health and Social Care, 2021). Finally, the UK COG has centralised data on COVID-19 variants allowing VE to reported by variant.

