9.3.3 Other Variables and Covariates

Table 6. Variable categories and data sources

Variables	Categories	Data source	Comment
Age	Different categorizations may be used -12 <50; 50-<65; 65-<70; 70-<80; 80+ -18-<40; 40-<50; 50+; 65+; 70+; 80+	GDPPR	BMI is binary as obese or not using HES, SUS, GDPPR or BMI can be created from weight/height if
Gender	Male/Female	-	available;
Ethnicity	White, Black, Asian, Other, Mixed		
Region	NHS Region	-	
Sociodemographic	Socioeconomic status – Index of Multiple Deprivation (IMD)		
BMI	-Obese (BMI 30+) -Not-obese (BMI <30)		
Smoking	- Current - Past - Non smoker		
Comorbidity	Specific comorbidities known to relate with increased risk of severe COVID- 19 and/or suboptimal vaccine response and/or vaccine contraindication including chronic respiratory disease, chronic kidney disease, chronic heart disease and vascular disease, chronic liver disease, chronic neurological disease, diabetes mellitus, severe mental illness, morbid obesity, asplenia or dysfunction of the spleen, and immunosuppression due to disease or treatment.	ORCIHD, HES and GDPPR	Follow JCVI/Green book list of comorbidities (COVID-19 Greenbook chapter 14a) Using ICD or SNOMED codes to identify comorbidities during the baseline period. For immunosuppressant medications, see Prescribed medication section below.
CMMS	0, and by quartile		Created from specific comorbidities;
Non-COVID-19 vaccination	 Flu vaccination (Y/N) Receive adequate vaccination (Y/N) 	GDPPR	An algorithm will be developed to determine if an individual is adequately vaccinated according to recommended vaccination schedule by age and comorbidity status
Prescription medication	Immunosuppressant vs. not	GDPPR	Prescribed medications at baseline will be grouped into immunosuppressant or not.
LTC /assisted living care facility	Yes/No	Not in any database	To be created for people aged 70+ by comparing their zip codes and LTC

Variables	Categories	Data	Comment
		source	
			address; or vaccination at LTC facility. (ORCHID)
Household composition	Size and age combination.	ORCHID UKHSA VE cohort	Available for 7.2 million subset of ORCHID
Frailty score	eFI grouped into - Mild - Moderate - Severe	Derived from GDPPR	Use an algorithm already developed to derive eFI, only available for population 65years and older. For this sub-group analysis.

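### Ethnicity, deprivation and influenza vaccination are collected but are in neither the matching nor the adjustment list, and no age term finer than a band is promised for the primary VE

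*Protocol*

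**What the plan says.** Protocol section 9.7.1 gives two explicit lists. Weekly 1:1 matching uses "age (study defined age bands), gender, general practice, (or NHS Region), and comorbidity as defined by CMMS quartile", chosen because they relate both to being vaccinated and to COVID-19 infection or severity. The Poisson model then estimates rates in the matched data, "adjusting for the matching variables and BMI, smoking, prescribed medications, and frailty score".

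Table 6 (section 9.3.3) also lists ethnicity ("White, Black, Asian, Other, Mixed"), deprivation ("Index of Multiple Deprivation (IMD") and influenza vaccination ("Flu vaccination (Y/N").

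Section 9.1 warns of controls near the end of life and says that "those who do not engage much with the health system may also be included"; it offers matching on age and other characteristics as the answer. Section 9.11.1 concedes that people who choose vaccination may differ from those who do not, and calls age adjustment critical. The limits of the matching age bands are not given.

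**The concern.** The protocol names its main threat, controls who differ in background and health-seeking, but its two lists leave out the collected variables that bear most directly on it. Influenza vaccination is the obvious available marker of engagement with preventive care. Ethnicity and deprivation plausibly relate to both vaccine uptake and severe COVID-19. If controls carry more of such risk, VE is overstated.

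Age raises a separate question. If it enters only as a band, and rollout within a band followed age, the newly vaccinated in a given week would tend to be older than those still unvaccinated, and a band term cannot remove that. VE would then be understated.

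Neither bias shrinks with sample size. Both could vary by age group and calendar time, and VE by age group and by time since dose is part of the primary objective.

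**Working it through.** **1. The lists side by side (Table 6 and section 9.7.1).**

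| Variable | In Table 6 | Matched | In Poisson model |
|---|---|---|---|
| Age | yes | in bands, limits not given | as a matching variable |
| Gender | yes | yes | yes |
| Practice, or NHS Region | region | yes | yes |
| CMMS quartile | yes | yes | yes |
| BMI, smoking, medication | yes | no | yes |
| Frailty (eFI) | yes, age 65 and over only | no | yes |
| Ethnicity | yes | no | no |
| IMD | yes | no | no |
| Influenza vaccination | yes | no | no |

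None of the last three appears in the subgroups of section 9.7.2 or the four sensitivity analyses of section 9.7.3. Below age 65 frailty cannot stand in for general health status.

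**2. The plan's only size figure.** Section 9.5 gives about 20 million people vaccinated and a 38% share for the study vaccine: 20,000,000 × 0.38 = 7.6 million, consistent with its statement of over 7 million. (The count and the share have different dates, so this is only a consistency check.) Random error will be small in the main analysis. As an illustration with assumed counts, take 1,000 events in vaccinees and 5,000 in controls over equal person-time. VE = 1 − 1,000/5,000 = 80%. The 95% limits use 1.96 × √(1/1,000 + 1/5,000) = 0.068 on the log scale, giving 78.6% to 81.3%.

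**3. An omitted binary trait.** The documents give no prevalences or risk ratios, so all inputs are assumed: prevalence pU = 30–50% in controls, pV = 15–20% in vaccinees, risk ratio r = 1.5–2.5.

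Factor = [1 + pV(r − 1)] / [1 + pU(r − 1)]; VE shown = 1 − (1 − true VE) × factor.

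- Weakest corner (pV 0.20, pU 0.30, r 1.5): 1.10/1.15 = 0.957
- Strongest corner (pV 0.15, pU 0.50, r 2.5): 1.225/1.75 = 0.70

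| True VE | Shown at 0.957 | Shown at 0.70 |
|---|---|---|
| 80% | 80.9% | 86.0% |
| 50% | 52.2% | 65.0% |
| 0% | 4.3% | 30.0% |

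Against the interval in step 2, the weak corner stays inside and the strong corner falls well outside.

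**4. A within-band age gap.** Assumed: vaccinees 1–3 years older than their matched controls, event rate doubling every 6–10 years. Factor = 2^(gap/doubling time), from 2^(1/10) = 1.07 to 2^(3/6) = 1.41. A true 80% shows as 79% down to 72%; a true 50% as 46% down to 29%.

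**5. Both together.** If the factors multiply, the extremes are 0.70 × 1.07 = 0.75 and 0.957 × 1.41 = 1.35. A true 80% then shows anywhere from 1 − 0.2 × 0.75 = 85% to 1 − 0.2 × 1.35 = 73%. The sign of the net bias is not determined.

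**The case against.** **The SAP may settle it.** Section 9.7.1 lets the SAP modify the plan. But the protocol is not silent here: it fixes both lists, and says that major changes to the analysis of the primary endpoints go through an amendment. The omission is a stated choice.

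**Balance checks are planned.** Love plots cover participants' characteristics, and summary tables of all characteristics are made before and after matching, so the three variables should already be displayed. This stands, and it would be wrong to infer that they go unexamined. Yet the only planned response is to refine the matching if differences look important; nothing brings the variables into the model.

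**Practice matching helps.** It absorbs part of area deprivation and ethnic mix. That also stands, but NHS Region is allowed instead, and individual health-seeking remains either way.

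**Age.** A reader might infer that matching uses bands as wide as those in Table 6 ("12 <50; 50-<65; 65-<70; 70-<80; 80", the last open-ended). The documents do not support that. Section 9.7.1 gives no limits; the printed bands belong to an example list of strata, a covariate table that permits other categories, and optional subgroups. Nor did rollout simply follow age: people aged 16 to 64 with comorbidities were recommended early vaccination (section 9.1), and carers and health care workers were early groups (section 4). Section 9.7.1 also plans linearity checks on continuous variables, and age might be one. What remains is narrower: no age term finer than the band is committed to.

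**Magnitude.** Every input is assumed, and the assumed gaps take no account of what practice, comorbidity, BMI, smoking, medication and frailty already remove.

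**Conclusion.** The point holds in limited form. Followed as written, the primary analysis leaves out three collected covariates that bear on the self-selection the protocol itself expects. It also commits to no age term finer than an unspecified band, so residual age differences are possible wherever rollout within a band followed age.

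The size is illustrative only. An omitted trait within the assumed ranges multiplies the rate ratio by 0.96 to 0.70, so a true VE of 80% shows as about 81–86%, 50% as 52–65%, and a null vaccine as 4–30%. A reader might conclude from this that the primary VE will be inflated. The documents do not show that, because an age gap with older vaccinees acts in the opposite direction and no input fixes either size. What can be said is that the bias is avoidable, that narrow intervals would not reveal it, and that the cost analysis in section 9.7.6.2 inherits it by mirroring the matching and most of the adjustment. The plan should be changed before the primary VE is run, but the study is not invalidated.

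**What to change.** In section 9.7.1, add ethnicity, IMD quintile and prior-season influenza vaccination to the Poisson model for the primary VE, and add age in single years, for example as a spline. State the season that defines the influenza variable, since Table 6 gives only yes or no. Carry the same covariates into the models of section 9.7.6.2.

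Leave the matching as planned. Matching age within about two years and relaxing practice to NHS Region to find pairs is tempting, but it would weaken the deprivation control sought here. It could also lose scarce older controls: section 9.1 reports over 90% of people aged 70 and over vaccinated by 22 March 2021.

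The cost is small. The variables are already listed for the dataset, and adding them to the model loses no matches by design. Some ethnicity data will be missing; the existing rule covers this (complete cases below 10% missing, multiple imputation in addition above it).
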